10.2 Reporting procedures for Adverse Events

Common non-life-threatening symptoms such as constipation, diarrhoea, colds, headache, etc. do not need to be reported for this study. Only adverse events **causally related** to the study procedures will be recorded and captured on the Adverse Events log within the participants' CRF. The following information will be recorded: description, date of onset and end date, severity, assessment of relatedness to study, other suspect device and action taken. Follow-up information should be provided as necessary. The relationship of AEs to the study will be assessed and signed off by a medically qualified individual who has been delegated the duty on the study Delegation of Authority and Signature Log.

AEs considered related to the study will be followed until resolution or the event is considered stable. All related AEs that result in a participant's withdrawal from the study or are present at the end of the study, will be followed up until a satisfactory resolution occurs.

It will be left to the investigator's clinical judgment whether or not an AE is of sufficient severity to require the participant's removal from treatment. A participant may also voluntarily withdraw from treatment due to what they perceive as an intolerable AE. If either of these occurs, the participant must undergo an end of study assessment and be given appropriate care under medical supervision until symptoms cease or the condition becomes stable.

The severity of events will be assessed on the following scale: 1 = mild, 2 = moderate, 3 = severe.

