3.2 Secondary objectives

The secondary objectives are:

- To measure the effect of a NMES programme on QoL
- To evaluate the cost-effectiveness of a NMES programme compared with standard care for patients with end-stage kidney disease within an NHS costing perspective
- To investigate if NMES results in neuromuscular adaptations and changes in muscle phenotype
- To measure the effect of a NMES programme on muscle size and measures of physical function
- To measure the safety of the intervention

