3.3.2 Secondary endpoints/outcomes

Secondary endpoints:

To compare between randomised groups;

- 1. Additional efficacy measures
 - a. Muscle size and architecture (measured cross-sectional area of rectus femoris using ultrasound, muscle thickness and angle of fibre pennation)
 - b. Lower-extremity strength, functional capacity, and balance: The short physical performance battery (SPPB)
 - c. Cardiovascular functional capacity and endurance: the 6-minute walk test (or incremental shuttle walk test in the event of space constraints)
 - d. Body composition (including lean muscle mass) using bioelectrical impedance
 - e. Sit-to-stand-60 test (muscle endurance)
 - f. GP Physical Activity questionnaire
 - g. Hand Grip strength
 - h. Accelerometry and sleep diary
 - i. Isometric rate of force development
- 2. Measures of QoL and social functioning
 - a. The Kidney Disease Quality of Life tool (KDQoL)
 - b. EQ-5D-5L, a generic multi-attribute health related QOL questionnaire for use in cost utility analysis (health economic analysis).
 - c. Levels of fatigue (using SONG-HD score)
 - d. SARC-F (validated questionnaire recommended as the screening instrument for sarcopenia in clinical practice by the European Working Group)
 - e. Sarcopenia and quality of life (SarQoL questionnaire)
- 3. NHS Resource use (collected via participant self-completion questionnaire), to be combined with NHS unit costs for use in cost utility analysis
- 4. Measures of process and tolerability
 - a. Number of patients eligible, approached and recruited
 - b. Dropout rates and movement between allocated study groups
 - c. Tolerability of the intervention to include number of neuromuscular stimulation sessions undertaken and the total time per session (up to 30-minutes).
- 5. Measures of safety
 - a. Adverse events relating to the intervention
- Measures of neuromuscular adaptations and muscle phenotype
 - High-density surfacer electromyography, for assessment of quadriceps motor unit recruitment and discharge rate, and conduction velocity during sub-maximum and maximum knee extension contractions.

- b. Intramuscular electromyography, for assessment of motor unit potential jiggle and segment jitter, electrophysiological markers of neuromuscular junction transmission stability.
- c. Femoral nerve stimulation, for assessment of quadriceps contractile properties.
- d. Skeletal muscle biopsy analysis

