8.4 Screening post consent

An inclusion criterion is the presence of sarcopenia which is determined by the presence of low muscle strength measured using a hand grip dynamometer (<27kg men and <16kg women). This will be determined after the participant has given consent. If their hand grip strength is found to be below these cut off thresholds, they will be eligible to take part in the study and will be randomised. If their hand grip strength is above these cut off thresholds, they are ineligible and will not be randomised.

As part of the Patient and Public Involvement work that we carried out prior to grant submission, patients suggested to include an opportunity to try the NMES procedure before they are randomised to see how well they are able to tolerate it. For those patients that are eligible, they will be offered the opportunity to try NMES on one occasion. The researcher will talk them through the procedure and explain which parameters will be changed and give the opportunity to control the different parameters to see how they find it. If patients do not think they will be able to tolerate the NMES they can withdraw from the study before they are randomised. As part of the screening visit, we will also familiarise people with the isometric strength measurement, our primary outcome measurement. This is to ensure they are able to complete this assessment with no problem and to eliminate any learning effects in the assessment visit.

8.5 Additional consent provisions for collection and use of participant data and biological specimens in ancillary studies

Not applicable for this study.

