8.6 Randomisation

After consent and baseline measurements have been collected, participants will be randomised by a delegated individual at each participating centre to either the intervention (3-months of NMES) or the control group (standard care) in a 1:1 manner. Participants will be allocated using minimisation factors of age and time on dialysis, this will ensure the external validity of the results.

Each participant will be given a unique participant ID number at randomisation. This participant ID number will be used to identify the individual participant throughout the study and will not be re-assigned to any other participant. Due to the nature of the intervention, blinding of the participants and the study team to the randomisation arm is not possible.

Randomisation will be performed using a validated web-based system to maintain allocation concealment. This will be managed by the Leicester Clinical Trials Unit.

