10. SAFETY REPORTING

10.1 Definitions

10.1 Definitions	
Term	Definition
Adverse Event (AE)	Any untoward medical occurrence in a patient or clinical investigation participants, which does not necessarily have to have a causal relationship with this treatment. An AE can therefore be any unfavourable and unintended sign (including an abnormal laboratory finding), symptom or disease temporally associated with the study, whether or not considered related to the study.
Adverse Reaction (AR)	An untoward and unintended response in a participant to an investigational medicinal product which is related to any dose administered to that participant. The phrase "response to an investigational medicinal product" means that a causal relationship between a trial medication and an AE is at least a reasonable possibility, i.e. the relationship cannot be ruled out. All cases judged by either the reporting medically qualified professional or the Sponsor as having a reasonable suspected causal relationship to the trial medication qualify as adverse reactions. It is important to note that this is entirely separate to the known side effects listed in the SmPC. It is specifically a temporal relationship between taking the drug, the half-life, and the time of the event or any valid alternative etiology that would explain the event.
Serious Adverse Event (SAE)	A serious adverse event is any untoward medical occurrence that: • results in death • is life-threatening • requires inpatient hospitalisation or prolongation of existing hospitalisation • results in persistent or significant disability/incapacity • consists of a congenital anomaly or birth defect Other 'important medical events' may also be considered serious if they jeopardise the participant or require an intervention to prevent one of the above consequences. NOTE: The term "life-threatening" in the definition of "serious" refers to an event in which the participant was at risk of death at the time of the event; it does not refer to an event which hypothetically might have caused death if it were more severe.
Serious Adverse Reaction (SAR)	An adverse event that is both serious and, in the opinion of the reporting Investigator, believed with reasonable probability to be due to one of the trial treatments, based on the information provided.

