10.3 Reporting Procedures for Serious Adverse Events

It is expected that participants will experience a significant number of underlying health conditions and consequently an increased number of expected hospital admissions. In addition, as this is an interventional study, expected events may occur related to the NMES intervention. NMES induces a muscle contraction via the delivery of a small electrical current. This may cause the muscles to feel sore the next day. There have been several previous studies of NMES in chronic disease patients, including haemodialysis patients that have reported very low rates of SAEs. A recent systematic review and meta-analysis performed by NICE has concluded NMES is safe to use in chronic disease population. Events may also be associated with the more invasive outcome measures such as the skeletal muscle biopsy and intramuscular electromyography. The muscle biopsy technique has been used successfully in many of our previous studies (REC ref: 13/EM/0344) and was well tolerated. The administration of local anaesthetic may cause mild discomfort, and there is a small risk of haemorrhage or infection at the biopsy site. Following the local anaesthetic, the procedure is not painful, though the biopsy site may ache for a day. Analgesia will be offered following the procedure. All biopsies will be performed by a doctor who is trained and has experience of the muscle biopsy procedure.

Therefore, only SAEs that are clearly related to the study procedures/intervention and of a serious nature will be subject to expedited reporting to the Sponsor. These SAEs include:

- Musculoskeletal injury as a direct result of the outcome assessments, skeletal muscle biopsy procedure, EMG, or the intervention (NMES)
- Anything else in the investigator's opinion that is related, serious, and unexpected.

These SAEs, occurring from the time of randomisation until end of assessment period, will be reported to the Sponsor immediately and within 24 hours of becoming aware of the event. The following information will be collected:

- full details in medical terms and case description
- event duration (start and end dates, if applicable)
- action taken
- outcome
- seriousness criteria
- relationship to the study procedure or intervention

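### Non-serious adverse events are listed for comparison between arms but recorded only if judged causally related, so that comparison is uninformative as specified

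*Protocol*

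**What the plan says.** All references are to the main randomised trial protocol, not the work package 1 protocol that precedes it.

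- **Endpoint (3.3.2).** The secondary endpoints stand under the lead-in "To compare between randomised groups". Item 5a, the only measure of safety in the list, is "Adverse events relating to the intervention".
- **Objective (3.2).** "To measure the safety of the intervention". No comparator is named. Section 3.4 gives 3 months after randomisation as the timepoint.
- **Recording rule (10.2).** "Only adverse events causally related to the study procedures will be recorded and captured on the Adverse Events log". Section 10.1 defines an adverse event more widely, as any untoward occurrence "whether or not considered related to the study".
- **Exposure of controls (8.4).** Before randomisation, eligible patients are told that "they will be offered the opportunity to try NMES on one occasion". Controls have no scheduled NMES after that.
- **Blinding (8.6).** "blinding of the participants and the study team to the randomisation arm is not possible".
- **Scheduled enquiry (7.1, 7.2).** Both arms have adverse event assessments at baseline, at each dialysis session in the intervention period, and at 3, 6 and 9 months.
- **Serious events (10.3).** Relatedness limits only expedited reporting. Other SAEs go on the SAE log, deaths are recorded, and all SAEs are tabulated by treatment group without formal testing.

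**The concern.** A randomised control group lets a trial separate treatment effects from background illness without relying on a clinician's opinion of cause in each case. That matters here: section 10.3 expects participants to carry considerable underlying illness, and NMES is given during dialysis, so individual attribution is difficult. For non-serious events the protocol applies the causality judgement before anything is recorded. Controls are asked about adverse events on the same schedule as the NMES arm, but an event they report is not logged unless someone attributes it to a study procedure.

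Two errors become possible. Background symptoms in the NMES arm that are put down to NMES would look like harm, because the same symptoms in controls leave no record. A real excess that is put down to dialysis or comorbidity would vanish from both columns. The analysis plan cannot repair either one, since the unrelated events never enter the adverse event log.

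**Working it through.** **Text against text**

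1. Item 5a counts events relating to the intervention. Controls have no NMES after randomisation apart from any crossover, so their count is about 0 of 114 by definition, whatever the true safety profile.
2. The 10.2 log is somewhat wider, because it admits events related to study procedures. Strength and walking tests, and optionally EMG, nerve stimulation and biopsy, occur in both arms, so control entries are possible but limited to those sources.
3. Section 10.2 asks for a relatedness assessment on each log entry, and 10.3 summarises events by relatedness. With only related non-serious events admitted, there is no unrelated category to set beside them.
4. Causality is signed off by a medically qualified delegate. Section 4 calls the trial assessor-blind, but nothing extends that to the causality judgement, and 8.6 says the study team cannot be blinded.
5. Section 11.3.4 treats every secondary outcome as continuous and analyses it by linear regression. That does not fit item 5a.

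**Size, by illustration**

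The protocol's only relevant figure is the arm size: 228 / 2 = 114. The total of 228 reproduces (102 per arm from a two-sided t-based calculation for 21.7 Nm with SD 47.5 Nm; 102 / 0.90 = 113.3, rounded up to 114) and is not in question. The documents give no adverse event rates, so every rate below is an assumption.

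Expected participants logged = 114 × true risk × share of events judged related. The true risk is set equal in both arms, so there is no harm to find. The 5% control figure stands for occasional attribution to shared assessments.

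| True risk, both arms | True number per arm | Logged, NMES (10% / 25% / 50% attributed) | Logged, control (0% / 5% attributed) |
|---|---|---|---|
| 20% | 22.8 | 2.3 / 5.7 / 11.4 | 0 / 1.1 |
| 40% | 45.6 | 4.6 / 11.4 / 22.8 | 0 / 2.3 |
| 60% | 68.4 | 6.8 / 17.1 / 34.2 | 0 / 3.4 |

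With no true effect, the log shows about 2 to 34 against 0, or against about 1 to 3 if a few control events are attributed.

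Now let NMES double a 20% risk. The truth is 114 × 0.40 = 45.6 against 114 × 0.20 = 22.8, an excess of 20 percentage points. If 10% of NMES-arm events and no control events are attributed, the log shows 45.6 × 0.10 = 4.6 against 0. The harmless case above, at 20% risk and 50% attribution, shows 11.4 against 0. The log can thus rank a harmless treatment as worse than a harmful one.

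If the events were recorded in both arms regardless of cause, the expected difference under no effect would be 0. The 95% confidence interval half-width is 1.96 × √(2p(1 − p)/114): 0.104 at p = 0.20 and 0.127 at p = 0.40 or 0.60, or about 10 to 13 percentage points.

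**The case against.** Related-only recording of non-serious events can be a proportionate choice in a population with heavy background illness. Several counterpoints stand.

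- A reader might infer that the safety objective cannot be answered at all. The documents do not support that. The objective names no comparator, and related events can be described within the NMES arm. All SAEs and deaths are recorded regardless of cause, SAEs are tabulated by arm, section 11.3.4 adds Kaplan–Meier displays for deaths and cardiovascular events, and the DSMC may advise on collecting further data.
- A reader might also infer that the whole control log is empty by construction. That holds only for NMES-related events.
- Nor is all non-serious information lost. SARC-F includes falls history and EQ-5D-5L includes pain or discomfort, both at baseline, 3, 6 and 9 months in both arms. They cover part of the ground but do not replace event recording.
- The lead-in in 3.3.2 is loose. It also covers recruitment counts and the number of NMES sessions, which cannot be compared between arms. A wording change would therefore remove the contradiction.
- The illustration is hypothetical. Very low attribution of local symptoms is unlikely, since 10.3 and 14.4 already lead staff to expect soreness after NMES.

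None of this makes the comparison of non-serious events informative. A wording change would settle the inconsistency, but the randomised comparison of those events would still be missing.

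**Conclusion.** The point holds for non-serious adverse events only. As specified, their between-group comparison mixes attribution with risk, and it cannot show an excess that staff judge unrelated. This follows from sections 3.3.2, 8.4, 8.6 and 10.2 together and needs no numerical assumption. The size does: about 2 to 34 logged NMES participants against 0 controls with no true harm, if true risk is 20% to 60% and 10% to 50% of NMES-arm events are attributed. Comparison of serious harms is intact. The matter should be corrected, and prospectively, because events never logged cannot be restored at analysis.

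**What to change.** **Preferred change.** In 10.2, add a short prespecified list of non-serious events that can occur in either arm. Candidates are thigh or leg muscle pain or soreness, thigh skin reaction, bruising or bleeding, falls, and symptomatic events during dialysis; the investigators should settle the final list. A skin item should refer to the thigh, not to electrode sites, or the control count is again about zero by definition. Record the listed events in both arms regardless of causality at assessments already scheduled, for example the 3-month visit that 3.4 gives as the safety timepoint, with relatedness as an attribute. Keep the related-only rule for everything else. Redefine item 5a as the number of participants with each listed event, and with any SAE, by randomised group.

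**Minimum change.** Take item 5a out of the between-group list, report related events descriptively for the NMES arm, and name all-cause SAEs as the comparative safety measure.

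**Either way,** exclude adverse events from the statement in 11.3.4 that all secondary outcomes are continuous.

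**Cost.** The minimum change is wording only. The preferred change adds modest data entry: at the 3-month visit alone, at most one short list for each of 228 participants. Using more of the scheduled assessments would reduce reliance on recall but add entry work, including for home dialysis patients. Self-reports would remain open to reporting bias because participants know their allocation.

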10.3 Reporting Procedures for Serious Adverse Events

It is expected that participants will experience a significant number of underlying health conditions and consequently an increased number of expected hospital admissions. In addition, as this is an interventional study, expected events may occur related to the NMES intervention. NMES induces a muscle contraction via the delivery of a small electrical current. This may cause the muscles to feel sore the next day. There have been several previous studies of NMES in chronic disease patients, including haemodialysis patients that have reported very low rates of SAEs. A recent systematic review and meta-analysis performed by NICE has concluded NMES is safe to use in chronic disease population. Events may also be associated with the more invasive outcome measures such as the skeletal muscle biopsy and intramuscular electromyography. The muscle biopsy technique has been used successfully in many of our previous studies (REC ref: 13/EM/0344) and was well tolerated. The administration of local anaesthetic may cause mild discomfort, and there is a small risk of haemorrhage or infection at the biopsy site. Following the local anaesthetic, the procedure is not painful, though the biopsy site may ache for a day. Analgesia will be offered following the procedure. All biopsies will be performed by a doctor who is trained and has experience of the muscle biopsy procedure.

Therefore, only SAEs that are clearly related to the study procedures/intervention and of a serious nature will be subject to expedited reporting to the Sponsor. These SAEs include:

- Musculoskeletal injury as a direct result of the outcome assessments, skeletal muscle biopsy procedure, EMG, or the intervention (NMES)
- Anything else in the investigator's opinion that is related, serious, and unexpected.

These SAEs, occurring from the time of randomisation until end of assessment period, will be reported to the Sponsor immediately and within 24 hours of becoming aware of the event. The following information will be collected:

- full details in medical terms and case description
- event duration (start and end dates, if applicable)
- action taken
- outcome
- seriousness criteria
- relationship to the study procedure or intervention

All other SAEs will be recorded using the SAE Log CRF. SAE data will be recorded on the REDCap database at regular intervals so that the LCTU can generate up-to-date reports for DSMC meetings. The DSMC will review the listings for clinical relevance and advise the TSC and Sponsor on the suitability of the continuance of the study following their review of the ongoing safety data and whether any further data should be collected or additional analyses undertaken.

Deaths will be recorded as part of the study outcomes and therefore will not be subject to expedited reporting.

SAEs will be reported using appropriate forms and according to the Sponsor SOP for reporting serious adverse events. Additional information will be provided if requested to the Sponsor and main Research Ethics Committee (REC). The Principal Investigator or another delegated physician (as agreed by the Sponsor) is responsible for the review and sign off of the SAE and the assessment of causality (i.e. whether an event is related to a study procedure or intervention).

The Sponsor will perform an initial check of the information and ensure that the SAE line listing is reviewed by the Director of Research & Innovation. All SAE information must be recorded on an SAE form and sent

to the Sponsor. Additional information received for a case (follow-up or corrections to the original case) needs to be detailed on a new SAE form and sent to the Sponsor.

Copies of all documentation and correspondence relating to SAEs will be stored in the TMF and/or ISF. Any change of condition or other follow-up information should be emailed to the Sponsor as soon as it is available or at least within 24 hours of the information becoming available. Events will be followed up until the event has resolved or a final outcome has been reached.

All SAEs will be tabulated and summarised by treatment group, according to system organ class and preferred term, as classified in the Medical Dictionary for Regulatory Activities (MedDRA). No formal statistical testing will be performed. All events will be summarised by seriousness, expectedness and relatedness.

The Sponsor will report all SUSARs to the Research Ethics Committee concerned. Fatal or life-threatening SUSARs must be reported within 7 days and all other SUSARs within 15 days. The CI will inform all investigators concerned of relevant information about SUSARs that could adversely affect the safety of participants.

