7.3 Reporting procedures for Serious Adverse Events

0968 STIM-HD WP1 Protocol Version 1.2 29 Jan 2025 IRAS: 347115

It is expected that participants will experience a significant number of underlying health conditions and consequently an increased number of expected hospital admissions. In addition, expected events may occur related to the NMES intervention. NMES induces a muscle contraction via the delivery of a small electrical current. This may cause the muscles to feel sore the next day. There have been several previous studies of NMES in chronic disease patients, including haemodialysis patients that have reported very low rates of SAEs. A recent systematic review and meta-analysis performed by NICE has concluded NMES is safe to use in chronic disease population.

Therefore, only SAEs that are clearly related to the study and of a serious nature will be subject to expedited reporting to the Sponsor. These SAEs include:

- Musculoskeletal injury as a direct result of the outcome assessments or the intervention (NMES)
- Anything else in the investigator's opinion that is related, serious, and unexpected.

These SAEs, occurring from the time of randomisation until end of assessment period, will be reported to the Sponsor immediately and within 24 hours of becoming aware of the event. The following information will be collected:

- full details in medical terms and case description
- event duration (start and end dates, if applicable)
- action taken
- outcome
- seriousness criteria
- relationship to the study procedure or intervention

All other SAEs will be recorded using the SAE Log, which will be kept in the Trial Master File.

Deaths will be recorded as part of the study outcomes and therefore will not be subject to expedited reporting.

SAEs will be reported using appropriate forms and according to the Sponsor SOP for reporting serious adverse events. Additional information will be provided if requested to the Sponsor and main Research Ethics Committee (REC). The Principal Investigator or another delegated physician (as agreed by the Sponsor) is responsible for the review and sign off of the SAE and the assessment of causality (i.e. whether an event is related to a study procedure or intervention).

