11.3.4 Analyses of secondary outcomes

The secondary outcomes will be analysed in a similar manner to the primary outcome. All represent continuous data and therefore linear regression will be used. All analyses will be adjusted for baseline value and the stratification factors. The number of deaths and cardiovascular events expected is relatively low, therefore formal time to event analyses will not be conducted. Kaplan–Meier will be presented to describe the relationship between these events and treatment.

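### Both protocols exempt every death, related or not, from expedited reporting, which contradicts their own 24-hour rule and leaves the 7-day fatal SUSAR report without a secured first step

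*Protocol*

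**What the plan says.** Section 10.3 of the main trial protocol restricts expedited reporting to serious events clearly related to the intervention or study procedures. It names musculoskeletal injury and then adds a general clause: "Anything else in the investigator's opinion that is related, serious, and unexpected". Such events "will be reported to the Sponsor immediately and within 24 hours of becoming aware of the event". All other SAEs go to the SAE log. The next paragraph but one then says: "Deaths will be recorded as part of the study outcomes and therefore will not be subject to expedited reporting". Later the same section sets the sponsor's duty to the ethics committee: "Fatal or life-threatening SUSARs must be reported within 7 days and all other SUSARs within 15 days".

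The Work Package 1 protocol, section 7.3, has the same list of expedited events, the same 24-hour deadline, the same sentence on deaths ("Deaths will be recorded as part of the study outcomes and therefore" exempt) and the same 7-day rule for fatal SUSARs.

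The definitions tables of both protocols (sections 10.1 and 7.1) make death the first criterion of seriousness.

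On outcomes, sections 3.3.2 and 3.4 of the main protocol list only adverse events relating to the intervention under safety, and 3.4 gives 3 months as the timepoint. Section 2 of Work Package 1 lists force, discomfort, exertion and soreness. The only analysis of deaths is in section 11.3.4 of the main protocol. It says "The number of deaths and cardiovascular events expected is relatively low", rules out formal time-to-event analysis and promises Kaplan-Meier curves.

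**The concern.** The sentence on deaths carries no qualifier. It covers a death caused by NMES, by a muscle biopsy or by maximal strength testing as fully as a death from background disease. A related, unexpected death is therefore on the 24-hour route by one rule and off it by another in the same section.

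At stake is the sponsor's ability to meet its own 7-day duty for fatal SUSARs. It cannot report to the ethics committee what a site has not yet told it. The text also produces an odd ordering: a related, unexpected event that threatens life must reach the sponsor within 24 hours, while the same event, if fatal at once, need not.

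**Working it through.** No figure in the plan bears on this point, so there is nothing to reproduce. The check sets the rules side by side.

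1. *Is a death an SAE?* Yes, by the first seriousness criterion in both definitions tables.

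2. *Which rule governs the first report from site to sponsor?* The rules are the same in section 10.3 (main trial) and section 7.3 (Work Package 1).

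| Event | Rule | Stated deadline, site to sponsor |
|---|---|---|
| Related, unexpected, life-threatening | Expedited list | 24 hours |
| Related, unexpected death, first known as a death | Expedited list | 24 hours |
| The same death | Sentence on deaths | None |
| Death following an SAE already reported | Follow-up rule | 24 hours from the new information |
| Unrelated death | Outside the expedited list in any case | None |

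Rows two and three are the contradiction.

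3. *What work does the sentence do?* The expedited list is already confined to related events, so the last row is the same with or without the sentence. Taken literally, the only cases it changes are related deaths.

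4. *Does the stated reason hold?* The sentence rests the exemption on deaths being study outcomes. In Work Package 1 nothing supports this: death is in no outcome list and no analysis. In the main trial it has thin support. Death is absent from the summary table and from sections 3.3.2 and 3.4, but section 11.3.4 plans a descriptive display of it. That same paragraph describes all secondary outcomes as continuous, which death is not. Even a genuine mortality endpoint would not explain why a death judged related to a study procedure should be exempt.

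5. *Does another route close the gap?* Both protocols require all SAE information to be put on an SAE form and sent to the sponsor, and a physician to assess causality. Neither states a deadline for that first form outside the 24-hour route. The 24-hour follow-up rule applies only where an SAE was reported before the death.

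6. *Consequence for the 7 days.* The sponsor's duty stands, but the step before it has no stated time limit once the sentence on deaths is applied. The text therefore does not guarantee that 7 days can be met.

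**The case against.** The best defence is that the passage can be read in order. Expedited events are defined first, the remainder goes to the log, and the sentence on deaths follows as a comment on that remainder. Section 10.3 opens by noting the heavy background morbidity of this population, so the authors probably meant background deaths, and the fatal SUSAR rule still binds. That is a plausible intention, and some sites would read it so. But the words do not say it, the reason given is outcome status and not background illness, and on this reading the sentence adds nothing.

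Three further objections stand in part:

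- SAE forms go to the sponsor under a sponsor SOP that is not shown and that may set a first-report deadline. If it does, the practical gap narrows, though sites would still hold a protocol sentence saying that deaths are not expedited.
- The documents do not say when the 7 days start, or that the report depends on the 24-hour route. The dependence is an inference, though a reasonable one.
- For the main trial it would be wrong to say that death is no outcome anywhere, given section 11.3.4. The accurate statement is that it is not a listed endpoint.

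A reader might infer that a related death would simply be logged until the next data safety monitoring committee meeting. The documents do not support that. The SAE form goes to the sponsor as well, and the committee meets when needed as well as at least once a year. A reader might also see in section 11.3.4 a need to add cardiovascular events to the endpoint lists. Definitions and data fields of that kind may be left to the SAP or case report form, and they have no bearing on expedited reporting.

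**Conclusion.** The point holds as an internal contradiction in a safety rule, present in both protocols. Read plainly, the sentence on deaths removes related deaths from the 24-hour route and leaves the 7-day fatal SUSAR report unsecured. In Work Package 1 the reason offered has no basis; in the main trial it rests on one descriptive analysis.

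The number affected cannot be given. It is tempting to multiply total follow-up by an assumed death rate, but that would count every death. Unrelated deaths would need no 24-hour report even without the exemption, so only related, unexpected deaths matter. The protocol gives no rate for these and cites very low SAE rates in earlier NMES studies. The expected count is probably very small; the weight of the point lies in the gravity of a single such case. No sample size, estimate or primary analysis changes.

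The conclusion assumes that the sponsor's SOP does not already set a first-report deadline for deaths, and that the SUSAR duty applies to NMES. On the latter, both definitions tables word SUSAR for a medicinal product, so its fit to a device event is itself not clear.

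**What to change.** - Main trial protocol, section 10.3: limit the exemption to deaths that the delegated physician has assessed as not related to the intervention or to any study procedure. State that any death with a possible relation follows the 24-hour route to the sponsor.
- Work Package 1 protocol, section 7.3: delete the sentence, since no outcome stands behind it, or limit it in the same way. Deleting it loses nothing, because unrelated deaths are already outside the expedited list.

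The cost is one sentence in each protocol and a prompt causality assessment of each death. Both sections already require a physician to assess causality for SAEs, so the added burden is mainly one of timing.
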